- 29. Participation in any investigational drug trial within 1 month or 5 half-lives of the investigational drug, whichever is longest, prior to Screening.
- 30. Participants currently receiving (or unable to stop using prior to receiving the first dose of IMP) medications or herbal supplements known to be potent inhibitors of CYP3A (must stop at least 1 week prior), potent inducers of CYP3A (must stop at least 3 weeks prior), or drugs mainly metabolized by CYP3A with a narrow therapeutic index (must stop at least 1 day prior).
- 31. History of or current alcohol or substance abuse
 - Excessive alcohol use is defined as alcohol and/or substance abuse or dependence (as defined by the Diagnostic and Statistical Manual of Mental Disorders, 5th edition) in the past year or a history of alcohol or substance abuse, as determined by the Investigator.
- 32. Clinically significant abnormality on ECG, or an active infective process or any other clinically significant abnormality on Screening CXR taken within 4 weeks of the first dose, per Investigator opinion. If a CXR has been taken within the previous 3 months and results are available and normal, the CXR does not need to be carried out.
- 33. eGFR by the 4-variable Modification of Diet in Renal Disease equation of <45 mL/min/1.73 m² or any renal condition that would preclude the administration of gadolinium (e.g., acute renal insufficiency).
- 34. ALT, AST, amylase, or lipase $> 2 \times$ above ULN of laboratory reference range, total bilirubin $> 1.5 \times$ ULN, any other clinically significant laboratory abnormality.
- 35. B cell (CD19) count < 50% of the LLN at Screening.
- 36. Significant cytopenia, including neutrophil count < 1,500/mm³, platelet count < 75,000/mm³, absolute lymphocyte count < 800/mm³, or a white blood cell count < 3500/mm³

Note: for participants participating in the OLE Period after receiving Tecfidera during the 48-week main study, absolute lymphocyte count < 800/mm³ is considered an exclusion criterion.

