5.4 Criteria for Randomization and Initiation of Trial Treatment

Randomization should occur on Day 1 after all Screening procedures have been completed; participant eligibility must be reviewed again and confirmed at the site on Day 1 prior to randomization. If a participant does not meet eligibility criteria, the participant can be retested and rescreened once after the approval of the Medical Monitor as described in Section 5.3.

Eligible participants will be randomized to treatment with M2951 (25 mg once daily, 75 mg once daily, or 75 mg twice daily), Tecfidera, or placebo through a central randomization process by an IWRS. Stratification will occur by region (USA or Western Europe, Eastern Europe and CCI, and RoW).

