5.6.1 Withdrawal from Trial Therapy

Participants who withdraw from therapy (during the 48-week main study or OLE Period) must immediately return for an End of Treatment Visit or an OLE End of Treatment Visit followed by the 4-week Safety Follow-Up/End of Trial Visit 4 weeks later (see Section 7.1.5 and 7.1.6). A participant must be withdrawn if any of the following occur:

- Withdrawn from study (see Section 5.6.2);
- AEs, if discontinuation of IMP is desired or considered necessary by the Investigator and/or participant;
- Use of prohibited medications, as defined in Section 6.4.2. However, any medications that are considered necessary for the participant's well-being may be given at the discretion of the Investigator. Use of a prohibited medication may be cause for a participant to withdraw, however each incident should be discussed on a case-by-case basis with the study and Medical Monitor;
- Pregnancy;
- Lack of efficacy and/or progression of MS as defined by Investigator judgment or when a medication other than protocol-allowed medications is needed for treatment;
- Any events that unacceptably endanger the safety of the participant;
- IMP will be discontinued in case of elevated liver tests as defined in protocol Section 6.4.4.
- If any of the following occur while a participant is receiving Tecfidera (17, 18):
 - Any instance of lymphocyte counts < 200/mm³ or < 500/mm³ for > 24 weeks
 - In the event of serious infection, Tecfidera should be withheld until the infection is resolved
 - At the first sign or symptom suggestive of PML
 - More than 1 instance of dose reduction due to a flushing reaction (see Section 6.4.4 or the local label [17, 18]) and GI disturbances.

Withdrawal due to special precautions is described in Section 6.4.4.

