6.4.2 Prohibited Medicines

Medications prohibited before the trial are listed in the exclusion criteria (Section 5.3.2).

[figure not shown]
The following medications and therapies are not permitted during the trial and would require discontinuation of the trial treatment:

- Initiation of an immunosuppressant or immunomodulator, such as cladribine, cyclophosphamide, azathioprine.
- New therapies for MS should not be initiated during the trial. Initiation of any new immunosuppressant or immunomodulatory therapy would be considered a treatment failure and should result in withdrawal of the participant from the IMP (see Section 5.6.1).

- Oral or parenteral steroids, except rescue medication to treat a relapse of MS, or adrenocorticotropic hormone. For participants experiencing a treatment gap (as described in Section 7.1.6), these medications can be administered only during that gap period if medically indicated, and must be discontinued prior to restarting study treatment.
- Biologic therapies.
- IV Ig therapy and/or plasmapheresis.
- Treatment with teriflunomide.
- Daclizumab.
- Live and live-attenuated vaccines.
- Medications known to lower the seizure threshold should be avoided. If treatment with these medications is required, the Investigator must inform the Medical Monitor.
- Initiation or dose changes of dalfampridine (Ampyra) or fampridine during OLE Period is permitted only in case the participant has been on a stable dose of evobrutinib for at least 3 months prior to initiation or dose change.
- Changes in dalfampridine dose (participant must be on a stable dose).
- Herbal supplements including, but not limited to, St. John's wort, grapefruit, Seville oranges, cranberries, or juices of these fruits.
- Any investigational drug within 1 month or 5 half-lives of the investigational drug, whichever is longest, prior to Screening.

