- Moderate or strong inhibitors or inducers of CYP3A or drugs mainly metabolized by CYP3A with a narrow therapeutic index. The list in Table 6 is not meant to be a complete list of all CYP3A inhibitors, inducers, or substrates with a narrow therapeutic range. Study sites should consider each medication on a case-by-case basis and discuss with the Medical Monitor. The additive effects of weak inhibitors taken in combination must also be taken into account. For participants experiencing a treatment gap (as described in Section 7.1.6), these medications can be administered only during that gap period if medically indicated, and must be discontinued prior to restarting study treatment.
- Any investigational drug or experimental procedure for MS.

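### Exclusion criterion 30 covers only potent CYP3A inhibitors and inducers, while Section 6.4.2 also prohibits moderate ones, so a participant can be randomised on a listed medicine

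*Protocol*

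**What the plan says.** **At entry.** Criterion 30 of Protocol Section 5.3.2 excludes people who are taking, or cannot stop before first dose, "medications or herbal supplements known to be potent inhibitors of CYP3A (must stop at least 1 week prior), potent inducers of CYP3A" (at least 3 weeks prior for the inducers), and narrow-therapeutic-index drugs mainly metabolised by CYP3A (at least 1 day prior). Moderate inhibitors and inducers are not named. Section 5.4 adds that "participant eligibility must be reviewed again and confirmed at the site on Day 1 prior to randomization".

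**On trial.** Section 6.4.2 first points back to the entry criteria: "Medications prohibited before the trial are listed in the exclusion criteria (Section 5.3.2"). It then introduces its own list: "The following medications and therapies are not permitted during the trial and would require discontinuation of the trial treatment". One item on that list is "Moderate or strong inhibitors or inducers of CYP3A or drugs mainly metabolized by CYP3A with a narrow therapeutic index". The same item refers to Table 6 as an incomplete list of examples and adds: "Study sites should consider each medication on a case-by-case basis and discuss with the Medical Monitor".

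**Consequence of use.** Section 5.6.1 places use of a Section 6.4.2 medicine among the events for which a participant must be withdrawn. It then qualifies this: "Use of a prohibited medication may be cause for a participant to withdraw, however each incident should be discussed on a case-by-case basis".

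**The concern.** Anyone who satisfies the entry criteria should be able to take the first dose without breaching the on-trial rules. Here one class of medicine breaks that link. A site that follows criterion 30 to the letter has no ground to exclude a candidate on a stable moderate CYP3A inhibitor or inducer, yet the same medicine is listed in Section 6.4.2 once treatment starts.

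Three things follow.

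- **Safety.** The protocol itself regards moderate agents as unsuitable alongside trial treatment, but does not visibly keep them out at first dose.
- **Consistency.** Three passages describe the consequence differently: treatment discontinuation required, participant must be withdrawn, and discussed case by case. Sites can reasonably act differently on the same facts.
- **Deviation handling.** It is unclear whether a person who met every entry criterion, and was already taking the medicine, is a protocol deviator from Day 1. It is also unclear whether that deviation is important enough to remove them from the Per-Protocol set.

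**Working it through.** No formula applies, and the plan states no figure on this point to reproduce. The check is a comparison of texts, followed by a search for anything that closes the gap. It reads potent in criterion 30 and strong in Section 6.4.2 as the same class; the protocol defines neither word.

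**1. Classes side by side**

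| CYP3A class | Excluded at entry (criterion 30) | Stop time in criterion 30 | Prohibited on trial (6.4.2) |
|---|---|---|---|
| Potent/strong inhibitors | Yes | 1 week | Yes |
| Potent/strong inducers | Yes | 3 weeks | Yes |
| Narrow-index substrates | Yes | 1 day | Yes |
| Moderate inhibitors | Not named | None | Yes |
| Moderate inducers | Not named | None | Yes |

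The mismatch is confined to the two moderate rows.

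**2. Does another passage close it?**

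- Section 6.4.2 sends pre-trial prohibitions back to Section 5.3.2, which is where the moderate class is missing.
- The Day 1 check in Section 5.4 confirms eligibility. No check against Section 6.4.2 is stated.
- Section 6.4.1 permits only medicines that the protocol does not prohibit, so it does not make a moderate agent acceptable.
- Section 6.4 has concomitant medicines recorded at Screening and Day 1. The site therefore sees the medicine before dosing, but no rule says what to do about it at that point.
- Inclusion criterion 6 requires willingness to comply with the protocol. This narrows the gap for a candidate who refuses to stop, but gives no interval.
- Table 6 is blacked out, so whether it grades agents or gives intervals cannot be seen.

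Nothing visible closes the gap.

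**3. Which analyses are touched?**

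- The primary analysis uses mITT (Section 8.5.2). Under Section 8.4 this needs randomisation, at least one dose, a baseline MRI and one post-baseline MRI. A prohibited co-medication does not remove anyone.
- The Per-Protocol set (Section 8.4) drops participants with important deviations or without 24 weeks of treatment. It is supportive only.
- SAP Section 10.1 lists receipt of an excluded concomitant medication as an important deviation. That SAP covers the final analysis only, where deviations exclude nobody. The analysis plan for the primary analysis is not among the documents, so how the deviation was graded there is unknown.

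**4. How many?** The documents give no rate of moderate CYP3A co-medication at entry, so no count follows.

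**The case against.** The best reply is that the text works as a two-stage safeguard. Criterion 30 screens out the strongest agents, and Section 6.4.2 leaves the rest to judgement with the Medical Monitor. The case-by-case sentence in Section 6.4.2 has no timing limit, so the discussion could take place before first dose. Part of this stands: withdrawal is not automatic, and a careful site may resolve the matter at Screening. It does not remove the conflict, because the same medicine is acceptable under the rule that decides entry and listed under the rule that governs treatment.

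It is also fair to say that the practical moment has passed. This is protocol version 8.0, the primary analysis is reported in Section 3.2, and rewording criterion 30 now changes nobody's entry. Amendment 6 revised the prohibited-medicines section, and the documents do not show whether moderate agents were listed while participants were being randomised. That limits what the point says about past conduct, but not the inconsistency in the current text.

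A reader might infer four stronger claims, none of which the documents support.

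- **Such participants must be discontinued from the first dose.** Sections 5.6.1 and 6.4.2 both make the outcome case by case.
- **No stop time for moderate agents exists anywhere in the plan.** Table 6 is redacted. It can only be said that criterion 30 gives none.
- **The evaluable sample is eroded.** One could assume that 2% to 5% of the 4 × 50 = 200 M2951 and placebo participants are affected, which gives 4 to 10, and set that against the 50 − 44 = 6 spare per arm. The rate is only an assumption, and those with the required MRIs remain in mITT, so 6 per arm is the wrong yardstick.
- **The dose-response comparison is distorted.** In the first 24 weeks only 3 × 50 = 150 participants receive M2951. Section 5.2.2 describes an exposure-response relation, but no figure shows how far a moderate agent shifts exposure. Randomisation balances entry co-medication in expectation.

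**Conclusion.** The point holds as an internal contradiction. Sections 5.3.2 and 6.4.2 use different CYP3A classes, and the moderate class is covered on trial but not at entry. A site following the text can randomise someone who is on a Section 6.4.2 medicine at first dose, and what then happens is left to discussion under passages that differ in force.

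The number affected cannot be estimated. The primary analysis set is largely insulated: someone who stopped before any post-baseline MRI (first scheduled at Week 12) could be lost from mITT, but the co-medication itself excludes nobody. The effect falls on participant safety, on whether and how deviations are classified, and on the supportive Per-Protocol analysis.

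The conclusion assumes that potent and strong mean the same class, and that the redacted Table 6 does not extend the entry rule. If potent was meant to include moderate agents, the intended rules may agree, but the wording still needs to say so.

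**What to change.** Reconcile Sections 5.3.2 (criterion 30), 5.6.1 and 6.4.2 in three respects.

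1. Use the same CYP3A class wording for entry and for treatment, so that anyone who passes criterion 30 is not on a listed medicine at first dose.
2. State a pre-dose stop time for every class on the joint list. The treatment-gap sentence in the CYP3A item of Section 6.4.2, which requires these medicines to be stopped before restart, also gives no interval and should be aligned.
3. State one consequence of use, in the same terms in Sections 5.6.1 and 6.4.2, and say how a medicine already being taken at Day 1 is classified as a deviation.

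Where the class boundary lies, and how long the intervals are, is for the sponsor's clinical team.

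The cost is a few sentences. With the main study enrolled, the change does not alter past eligibility; its use now is in consistent handling and reporting of deviations. Since concomitant medicines were recorded at Screening and Day 1, the sponsor could also count the participants who were on a moderate agent at first dose and report how they were handled, which would supply the missing size.

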5.4 Criteria for Randomization and Initiation of Trial Treatment

Randomization should occur on Day 1 after all Screening procedures have been completed; participant eligibility must be reviewed again and confirmed at the site on Day 1 prior to randomization. If a participant does not meet eligibility criteria, the participant can be retested and rescreened once after the approval of the Medical Monitor as described in Section 5.3.

Eligible participants will be randomized to treatment with M2951 (25 mg once daily, 75 mg once daily, or 75 mg twice daily), Tecfidera, or placebo through a central randomization process by an IWRS. Stratification will occur by region (USA or Western Europe, Eastern Europe and CCI, and RoW).

5.5 Criteria for Entry into OLE Period

Participants who have withdrawn after randomization (e.g., due to AEs or lack of efficacy) will not be replaced and will not be eligible to participate in the OLE Period. Only participants who have completed the 48-week main study are eligible to participate in the OLE Period. Participants who entered the OLE Period initially received M2951 at 75 mg once daily. After review of the efficacy and safety data from the primary analysis at 24 weeks and the blinded extension analysis at 48 weeks, the optimal tested dose is 75 mg twice daily. Accordingly, once IMP for this dose is available at the study site, participants participating in the OLE Period will either enter the OLE Period on the 75 mg twice daily dose or will be switched to the 75 mg twice daily dose.

5.5.1 Participants Entering OLE Period after Receiving Tecfidera

For participants who received Tecfidera during the 48-week main study and choose to enter the OLE Period, there should be a minimum 4-week washout period before starting open-label M2951 (Table 5). If a participant who received Tecfidera has an absolute lymphocyte count $< 800/\text{mm}^3$ 4 weeks after discontinuing Tecfidera, M2951 treatment should not be initiated. If the participant's absolute lymphocyte value reaches $\ge 800/\text{mm}^3$ after 8 weeks of discontinuing Tecfidera, he or she may begin M2951 treatment in the OLE Period, and the OLE Day 1 Visit should be scheduled within 1 week. During this washout period, a participant may continue to be monitored for absolute lymphocyte count values (at Tecfidera Washout Visit 1 or 2) or may discontinue the study and begin a different treatment regimen in agreement with the Investigator. If a participant is not eligible to enter the OLE Period by Tecfidera Washout Visit 2, he or she will need to return for the End of Trial Visit described in Section 7.1.8. This End of Trial Visit should be completed within 14 days \pm 7 days from the time the decision is reached that the participant is not eligible to enter the OLE Period.

Table 5 Washout Period for Participants on Tecfidera Treatment Arm before Entering OLE Period

Activity/Assessment	Tecfidera Washout Visit(s)			
Visit number (for Washout Period)	Tecfidera WO 1	Tecfidera WO 2 ^{a,b}		
Tecfidera Washout Week	W4	W8		
Tecfidera Washout Day ± Visit Window ^c	28 ± 7	56 ± 7		
Absolute lymphocyte count ^d	Х	X		
Relapse assessment	X	X		

OLE=Open-label Extension, WO=washout.

- a. Tecfidera Washout Visit 2 will occur only if the participant has an absolute lymphocyte count < 800/mm³ at Tecfidera Washout Visit 1.
- b. If a participant is not eligible to enter the OLE Period by Tecfidera Washout Visit 2, he or she will need to return for the End of Trial Visit described in Table 1. This End of Trial Visit should be completed within 14 days ± 7 days from the time the decision is reached that the participant is not eligible to enter the OLE Period.
- ^{c.} Tecfidera washout visits will occur within the range of days noted for each week following end of treatment with Tecfidera.
- d. Treatment with M2951 will only commence if a participant who received Tecfidera during the 48-week main study has an absolute lymphocyte count ≥ 800/mm³ following 4 weeks of washout. If the participant does not have an absolute lymphocyte count ≥ 800/mm³ at Tecfidera Washout Visit 2, he or she will be excluded from the OLE

Period. At any time during the washout period, the participant may choose to discontinue from the study and begin a different treatment regimen in agreement with the Investigator.

5.6 Criteria for Participant Withdrawal

Participants will be informed that they have the right to withdraw from the trial at any time, without prejudice to their medical care, and they are not obliged to state a reason for withdrawing. Any withdrawal must be fully documented in the eCRF and source documents, and should be followed up by the Investigator.

The Investigator may withdraw a participant at any time if this is considered to be in the participant's best interest.

5.6.1 Withdrawal from Trial Therapy

Participants who withdraw from therapy (during the 48-week main study or OLE Period) must immediately return for an End of Treatment Visit or an OLE End of Treatment Visit followed by the 4-week Safety Follow-Up/End of Trial Visit 4 weeks later (see Section 7.1.5 and 7.1.6). A participant must be withdrawn if any of the following occur:

- Withdrawn from study (see Section 5.6.2);
- AEs, if discontinuation of IMP is desired or considered necessary by the Investigator and/or participant;
- Use of prohibited medications, as defined in Section 6.4.2. However, any medications that are considered necessary for the participant's well-being may be given at the discretion of the Investigator. Use of a prohibited medication may be cause for a participant to withdraw, however each incident should be discussed on a case-by-case basis with the study and Medical Monitor;
- Pregnancy;
- Lack of efficacy and/or progression of MS as defined by Investigator judgment or when a medication other than protocol-allowed medications is needed for treatment;
- Any events that unacceptably endanger the safety of the participant;
- IMP will be discontinued in case of elevated liver tests as defined in protocol Section 6.4.4.
- If any of the following occur while a participant is receiving Tecfidera (17, 18):
 - Any instance of lymphocyte counts < 200/mm³ or < 500/mm³ for > 24 weeks
 - In the event of serious infection, Tecfidera should be withheld until the infection is resolved
 - At the first sign or symptom suggestive of PML
 - More than 1 instance of dose reduction due to a flushing reaction (see Section 6.4.4 or the local label [17, 18]) and GI disturbances.

Withdrawal due to special precautions is described in Section 6.4.4.

5.6.2 Withdrawal from the Trial

Participants may withdraw from the trial at any time without giving a reason. Withdrawal of consent will be considered withdrawal from the trial. Participants who withdraw from the trial while still on the IMP should return immediately for an End of Treatment Visit upon discontinuation of the IMP and a Safety Follow-Up/End of Trial Visit 4 weeks after the last administered dose of IMP. Participants who withdraw and are no longer on the IMP must complete the 4-week Safety Follow-up/End of Trial Visit assessments described in Section 7.1.8.

A participant must be withdrawn if any of the following occur during the trial:

- Pregnancy (for further details in case of pregnancy, see Section 7.4.2);
- Participant withdrew consent;
- Participation in another clinical trial;
- Lost to follow-up;
- Any events that endanger the safety of the participant;
- Sponsor decision to end clinical trial.

If a participant fails to return for the post-treatment safety visit, all attempts should be made to contact the participant to ensure the reason for not returning is not an AE. Likewise, if a participant wishes to discontinue from the trial (e.g., for personal reasons), attempts should be made to establish the true reason is not an AE (bearing in mind the participant is not obliged to state the reasons).

If IMP is prematurely discontinued, the primary reason for discontinuation must be recorded in the appropriate section of the eCRF, and all efforts will be made to complete and report the observations as thoroughly as possible. A complete final evaluation at the time of the participant's withdrawal should be made and any AEs followed up until resolution or a period of 30 days after the last Safety Visit (or withdrawal from the trial).

If a participant has failed to attend scheduled trial assessments, the Investigator must determine the reasons and the circumstances as completely and accurately as possible.

Participants who have withdrawn after randomization (e.g., due to AEs or lack of efficacy) will not be replaced and will not be eligible to participate in the OLE Period. Only participants who have completed the 48-week main study are eligible to participate in the OLE Period. Participants who are withdrawn from the trial will not be allowed to re-enroll in the trial.

Participation in any other trial during the duration of this trial (including the OLE Period) will not be allowed.

At least 3 attempts to contact lost to follow-up participants should be made and documented (2 phone calls and 1 acknowledgement of receipt letter).

The Investigator should permanently discontinue study treatment upon confirmation of noncompliance regarding study treatment (see Section 6.8) or extended interruption of the study treatment for more than 30 days.

